7.9.1. Participant Attrition

Participants meeting the inclusion criteria and not meeting the exclusion criteria will be summarized using frequency and percentage for the cohort selected. A STROBE flow diagram⁴⁴ will be used to visualize sample size for the study population and cohort assignment.

7.9.2. Analysis of Baseline Characteristics

Descriptive analysis will be conducted to describe baseline demographic and clinical characteristics of the Roctavian and SoC Cohorts. See Table 3 for a list of all variables that will be described for the two Cohorts. The baseline characteristics will capture data before the index date.

Measures of central tendency and dispersion (mean, SD, median) will be calculated and reported for continuous variables for each Cohort. Continuous variables may be categorized into intervals, with the distribution of participants (n, %) provided. Independent sample t-tests for mean values and Wilcoxon rank-sum tests for median values will be performed as a comparison between the Roctavian and SoC Cohorts.

For categorical variables, distributions and frequencies will be compiled and reported. Data will include the frequency (n, %) of total participants observed in each category. Chi-square tests will be performed as a comparison between the Roctavian and SoC Cohorts.

SMD will be calculated for both continuous and categorical variables. SMD represents a commonly used statistic to examine the balance of covariate distribution between groups, with a value greater than 0.1 indicating some imbalance between groups, and SMDs >0.25 indicating poor balance.⁴⁵

Participant characteristics will be presented for all participants prior to weighting and after weighting (for Roctavian and SoC Cohorts separately), overall, and for subgroups and sensitivity analyses where appropriate. Participant characteristics prior to and after weighting will be compared using the statistical tests noted above to capture differences between the observed population and the weighted target population.

7.9.3. Analysis of Primary Outcome

Population	Measurement Period	Analysis Notes
All participants For interim and analyses at fixed timepoints, only those with specified amounts of follow-up will be included	≥1 year of follow-up, ≥2 years of follow-up, ≥3 years of follow-up, all available follow-up	Participants with no bleeds will be included as having an ABR of 0

The primary objective to compare the ABR for treated bleeds between the Roctavian and SoC Cohorts will be measured by annualizing the number of bleeds reported in the DHR. Follow-up for ABR will begin as of the index date for the SoC and Roctavian Cohorts. Bleeds will be identified if participants have an “occasion” for treatment of spontaneous bleeding/hemorrhage (regardless of severity). Participants may have multiple bleeds during the reporting period. To calculate ABR, a count of the number of bleeds for each participant will be divided by the number of days in the relevant time period for each participant, multiplied by 365.25. The mean of the individual ABRs for each Cohort will be calculated and then compared between Cohorts over the full follow-up time, as well as during annual increments during the follow-up. For analyses of annual increments, only those participants with full follow-up for that timepoint will be included. For example, analyses comparing ABRs during the first year will only include participants with ≥1 year of follow-up after the index date or analyses comparing ABRs through two years of follow-up will only include participants with ≥2 year of follow-up after the index date. Sample sizes are expected to be reduced in analyses of annual increments for interim analyses as data collection will be ongoing.

Mean, SD, median, IQR, minimum and maximum will be reported for the primary outcome by study group. Histograms will be plotted for the primary outcome by study group. SMD will be calculated to compare Roctavian and SoC Cohort. The participant number in the two Cohorts will be weighted using IPTW generated from the propensity score model. Both unadjusted and propensity score adjusted results will be reported and compared.

Given treated bleeds are event based, a IPTW weighted negative binomial model will be fit to compare ABR between Roctavian and SoC Cohort, with negative binomial distribution and log link function, and the log transformed follow-up time as the offset variable. IPTW will be applied to create

more similar Roctavian and SoC Cohorts. Other clinically significant prognostic factors or covariates that remain imbalanced after propensity score adjustment will be included in the model as well. Regression coefficients, corresponding 95% CIs and p-values will be reported for all explanatory variables included in the model. The estimated rate ratio (ABR in Roctavian Cohort / ABR in SoC Cohort) generated from the IPTW weighted negative binomial model will be tested against the shifted null hypothesis of 0.5. For an alpha=0.025 test, the shifted null hypothesis is rejected if the upper boundary of the two-sided 95% CI for the rate ratio is less than the null hypothesis 0.5. The CI of the estimated rate ratio will be calculated using the Wald method.²⁷

Given some participants may have no treated bleeds based on prior literature,⁴⁶ a two-part zero-inflated negative binomial model will also be considered. If the negative binomial model does not converge,⁴⁷ or if the AIC in the model accounting for zero-inflation is lower, then the zero-inflation negative binomial model will become the primary objective analytic model, as lower AIC indicates a better fit. For the zero-inflated negative binomial model, first the model will be fit for a binary outcome whether a participant had a treated bleed during the outcome assessment period, and then an ABR count outcome for treated bleeds among participants who had at least one treated bleed during the outcome assessment period (excluding participants with zero bleeds) will be fit. Finally, the unconditional ABR estimates for treated bleed will be calculated by multiplying the estimated conditional ABR from the count model by the probability of having a treated bleed estimated from the binary model for both the Roctavian and SoC Cohorts.

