7.6. Study Sample Size

The primary goal of HA treatment is to reduce the bleeding rate or to achieve freedom from bleeding. As an approximation of the appropriate number of cases for the data collection accompanying the application, the Institute for Quality and Efficiency in Health Care (IQWiG) conducted the sample size calculation based on ABR for treated bleeds. Evaluation of the ABR is performed using a negative binomial model.

The formula for The sample size calculation is as follows:

$$N_1 \geq \frac{(z_\alpha \sqrt{V_0} + z_\beta \sqrt{V_1})^2}{(\log(R_0) - \log(\lambda_2/\lambda_1))^2}$$

$$N_2 = \theta N_1$$

Where:

$$V_1 = \frac{1}{\mu_t} \left(\frac{1}{\lambda_1} + \frac{1}{\theta \lambda_2} \right) + \frac{(1 + \theta)\varphi}{\theta}$$

V_0 is computed using the fixed marginal total method, the 2nd method recommended by Zhu et al.:²⁷

$$V_{02} = \frac{(1 + R_0\theta)^2}{\mu_t R_0 \theta (\lambda_1 + \theta \lambda_2)} + \frac{(1 + \theta)\varphi}{\theta}$$

N_1 is the sample size for control, N_2 is the sample size for intervention. $\theta = \frac{N_2}{N_1}$, which is the sample size ratio; R_0 is the superiority margin ratio at the null hypothesis. In this case, R_0 is <1 since higher rates are worse. λ_1 is the event rate in the control group, and λ_2 is the event rate in the intervention group. φ is the dispersion parameter, and μ_t is the average exposure time. z_α is the z-score at the significance level, z_β is the z-score at the power value.

When higher rates are worse, the superiority by a margin test hypotheses are

$$H_0: \frac{\lambda_2}{\lambda_1} \geq R_0 \quad \text{vs.} \quad H_1: \frac{\lambda_2}{\lambda_1} < R_0$$

Where $R_0 < 1$.

The relative effect measure is the incidence rate ratio of Roctavian over SoC, which can be tested against the shifted null hypothesis of 0.5, assuming a significance level $\alpha = 2.5\%$ with a one-sided test, and power of at least 80%. Higher values for the ABR (parameter λ) stand for a worse outcome. Furthermore, a distribution of the Sample Roctavian vs. SoC of 1:5 is assumed (sample size ratio $\theta = 0.2$). Other required parameters are the Average Exposure Time ($u_t = 1$ year), the ABR for the SoC and Roctavian groups ($\lambda_{SoC} = 3$, $\lambda_{Roctavian} = 0.85$) and a value for the overdispersion ($\phi = 1.5$). This results in a total sample size of at least 397 participants (Roctavian Cohort $n = 67$, control Cohort $n = 330$).

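### The fallback for the primary endpoint is labelled zero-inflated but described as a two-part model on bleeders, and it yields no confidence interval for the rate ratio that the 0.5 rule needs

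*Protocol*

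**What the plan says.** SAP section 7.9.3 compares treated bleeds with a weighted negative binomial model that has log follow-up time as offset. The Roctavian/SoC rate ratio from that model is tested against 0.5. The shifted null is rejected if the upper limit of the two-sided 95% Wald interval lies below 0.5.

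The same section then introduces a two-part zero-inflated alternative. If the negative binomial model does not converge, or if the alternative has the lower AIC, "the zero-inflation negative binomial model will become the primary objective analytic model". The steps given for it are:

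- a binary model for whether a participant had any treated bleed;
- a count model "among participants who had at least one treated bleed during the outcome assessment period (excluding participants with zero bleeds) will be fit";
- an unconditional ABR for each cohort, obtained by "multiplying the estimated conditional ABR from the count model by the probability of having a treated bleed estimated from the binary model".

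No ratio, variance method, interval or test follows. The offset is stated only for the plain negative binomial model. The SAP table shell for the ABR regression (Table 6) covers negative binomial regression only. SAP section 7.9.4.1 carries the same model choice over to major, life-threatening and joint bleeds.

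**The concern.** A zero-inflated model is a mixture fitted to everyone. Its count part can itself produce zeros, so participants without bleeds stay in it. Splitting the sample into bleeders and non-bleeders and fitting counts to the bleeders is a two-part, hurdle-type model. Label and description therefore point to different analyses, and two programmers could build different primary results from the same text.

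The larger problem is the test. The only interval tied to the 0.5 rule belongs to a coefficient of the plain negative binomial model. Under the fallback the quantity of interest is a ratio of two products, and the Wald interval of one coefficient is not an interval for that ratio. The fallback can become the primary model on an AIC difference alone, so the primary hypothesis could be left without a prespecified test.

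**Working it through.** **Inputs.** SAP section 7.6: ABR 3 (SoC) and 0.85 (Roctavian), so the true ratio is 0.85/3 = 0.283; dispersion φ = 1.5; θ = 0.2; one-sided α 0.025; power 80%; average exposure 1 year; the ratio "can be tested against the shifted null hypothesis of 0.5". The documents give no expected distribution of follow-up, so the follow-up patterns below are assumptions.

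**The plan's own figure.**
- V1 = 1/3 + 1/(0.2 × 0.85) + 1.2 × 1.5/0.2 = 15.216.
- V0 = 1.1²/(0.5 × 0.2 × 3.17) + 9 = 12.817.
- N1 = (1.960√12.817 + 0.8416√15.216)² / (ln 0.5 − ln 0.283)² = 328.8.

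This rounds to 329 SoC and 66 Roctavian, 395 in total against the stated 397. Power at 330 SoC is 0.801. The planning figure holds, and this point does not change it.

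**Zeros expected without zero inflation.** P(0) = (1 + φλT)^(−1/φ).

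| | SoC | Roctavian |
|---|---|---|
| 1 year | 0.321 | 0.578 |
| 3 years | 0.168 | 0.350 |

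Many zeros alone therefore do not show zero inflation.

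**The count-part ratio.** The mean yearly rate among bleeders is λ/(1 − P(0)).
- 3 years: SoC 3/0.832 = 3.607; Roctavian 0.85/0.650 = 1.308; ratio 0.363.
- 1 year: SoC 3/0.679 = 4.418; Roctavian 0.85/0.422 = 2.015; ratio 0.456.

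Both differ clearly from 0.283.

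**The product.** Take one reading: an untruncated negative binomial with log-time offset fitted to bleeders, and no exposure term in the binary part. Simulation with 400,000 participants per arm gave:

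| Follow-up | Ratio, true 0.283 | Ratio, true 0.5 |
|---|---|---|
| All 1 year | 0.284 | 0.500 |
| All 3 years | 0.285 | 0.498 |
| Both cohorts 1, 2 or 3 years | 0.274 | 0.494 |
| SoC 3; Roctavian 0.5, 1.5 or 3 | 0.253 | 0.467 |
| SoC 0.5, 1.5 or 3; Roctavian 3 | 0.293 | 0.514 |

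In the fourth row the Roctavian product is 0.758 against 0.85, a factor of 0.89. In the fifth the SoC product is 2.906 against 3, a factor of 0.97.

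The mechanism is that longer follow-up makes a bleed more likely, so bleeders have longer follow-up than the cohort. If the count part were total bleeds over total time among bleeders, product/true would be mean(T)/mean(T given a bleed). For Roctavian at 1 or 3 years in equal shares, this is 2/[(0.422 × 1 + 0.650 × 3)/(0.422 + 0.650)] = 0.904. This formula somewhat overstates the bias of a negative binomial fit: for Roctavian at 1, 2 or 3 years it gives 0.935, against a simulated 0.814/0.85 = 0.958.

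**Dispersion.** In the same fits the estimated dispersion was 0.03 to 0.84 instead of 1.5, with equal and unequal follow-up alike. Model-based Wald standard errors from such a fit are not reliable.

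**The switching rule.** In 300 unweighted trials of 67 and 330 per follow-up pattern, with truly negative binomial data, the AIC rule chose the two-part model in 3% to 14% of trials when the count part was zero-truncated, and in none when it was not. The unspecified detail also decides when the fallback takes over.

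**The case against.** Several things limit the point.

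- The SAP does not say the count part is untruncated. It uses the words two-part and cites a text on two-part models, and a conditional ABR times a probability is also how a correct zero-truncated hurdle model would be summarised. This stands: the finding is a wrong label and an incomplete specification, not a proven wrong fit.
- If the count part means the average of individual ABRs among bleeders, then P(bleed) × mean(ABR given a bleed) equals the cohort mean ABR whatever the follow-up. This also stands: the product bias needs an offset in one part and no exposure term in the other.
- Each participant is planned to have 3 years, little loss to follow-up is expected, and the treatment policy analysis keeps Roctavian participants after they resume prophylaxis. Follow-up may then be nearly equal at the final analysis. It is variable at the 36- and 54-month interims, and under the hypothetical estimand Roctavian follow-up starts later and is censored at resumption.
- With truly negative binomial data, AIC never selected the untruncated version. Non-convergence or genuine zero inflation could still bring it in.

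A reader might infer that the bias always favours Roctavian. It does not: the ratio falls when Roctavian follow-up is the more variable and rises when SoC follow-up is. A reader might also infer that the 0.5 rule can only be applied to the ratio among bleeders. The text does not force that. It defines the rate ratio as Roctavian ABR over SoC ABR, and the fallback supplies both unconditional ABRs. What is missing is the interval.

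None of these objections supplies that interval.

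**Conclusion.** The point holds in limited form. SAP section 7.9.3 names one model and describes another, leaves truncation and exposure handling open, and lets the result become the primary analysis without an interval for the ratio that the 0.5 rule tests. The missing interval and the wrong label follow from the text alone.

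The numerical consequences are conditional. If an ordinary negative binomial is fitted to bleeders only, its dispersion and Wald standard errors are wrong. If it also has an offset while the binary part has no exposure term, unequal follow-up shifts a cohort's product by a few percent up to about a tenth; the direction of the shift in the ratio depends on which cohort's follow-up varies. With equal follow-up there is essentially no bias. These sizes rest on the planning rates, φ = 1.5, unweighted data and assumed follow-up patterns.

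Separately, protocol section 10.1 says the tested null hypotheses are not shifted, and section 10.3.6.1 makes a t-test on mean ABRs the primary comparison. The 0.5 rule has to be reconciled with both, but doing so would not repair the fallback.

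**What to change.** Replace the two-part description in SAP section 7.9.3 with one correctly specified model:

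- a true zero-inflated negative binomial fitted to all participants with log follow-up as offset; or
- a hurdle model with a zero-truncated count part and follow-up in both parts, where the conditional mean is that of the truncated distribution.

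Define the marginal rate ratio as the unconditional Roctavian ABR divided by the unconditional SoC ABR. Take its 95% interval from a bootstrap that re-estimates the propensity weights in each resample, and apply the 0.5 rule to that interval. Make the same change for the secondary ABRs in section 7.9.4.1 and add a matching table shell.

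The cost is SAP wording, one shell and a bootstrap step. Sample size and data collection are unaffected.

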7.9.4. Analysis of Secondary Outcomes

The secondary outcomes include other major, life-threatening, and joint ABRs, treatment outcomes, COAs, and safety outcomes. All outcomes will be compared between the Roctavian and SoC Cohorts.

7.9.4.1. ABR for Major, Life Threatening, and Joint Bleeds

Population	Measurement Period	Analysis Notes
All participants For interim and analyses at fixed timepoints, only those with specified amounts of follow-up will be included	≥1 year of follow-up, ≥2 years of follow-up, ≥3 years of follow-up, all available follow-up	Participants with no bleeds will be included as having an ABR of 0

As outlined in Section 7.9.3, ABR will also be calculated for major, life threatening, and/or joint bleeding events. For each bleed type, ABR will be calculated by dividing the total number of bleeds in each Cohort with the respective bleed type by the number of days in the reporting window for all participants in that Cohort, multiplied by 365.25. ABR of each Cohort will be compared over the full follow-up time for each participant in the study, as well as during annual increments during the follow-up period.

Similar to the analytic approach for the primary outcome, an IPTW weighted negative binomial model or a IPTW weighted zero-inflated negative binomial model, whichever appropriate (based on the rules applied in the primary objective Section 7.9.3), will be fit to compare each ABR measure between Roctavian and SoC Cohorts. IPTW will be applied to create more similar Roctavian and SoC Cohorts. Other covariates that remain imbalanced after propensity score adjustment will be included in the model as well. Regression coefficients, corresponding 95% CIs and p-values will be reported for each explanatory variables included in the model.

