7.9.4.2. Proportion of Participants with Zero Bleeds

Population	Measurement Period
All participants	≥1 year of follow-up, ≥2 years of follow-up, ≥3 years of follow-up, all available follow-up

For interim and analyses at fixed timepoints, only those with specified amounts of follow-up will be included	
---	--

The proportion of participants who had no bleeding events of each of the following types will be reported and compared between the Roctavian and SoC Cohorts: treated bleeds, major bleeds, life threatening bleeds, and joint bleeds. The approach will be generally consistent with the analysis approach for ABRs (see Section 7.9.3) regarding the adjustment approach (IPTW), analysis of the full follow-up period along with annual increments and start of follow-up period.

The binary outcomes will be analyzed using propensity score IPTW weighted log binomial regression models. The main predictor of interest is the treatment effect (Roctavian vs. SoC), other imbalanced covariates after propensity score adjustment may be included in the model as necessary. The risk ratio (relative risk), corresponding 95% CIs and p-values will be reported.

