7.9.4.5. Safety Events

Population	Measurement Period	Analysis Notes
All participants	All available follow-up data	
Safety events will be compared between the Roctavian and SoC Cohorts
 
Due to the possibility of unknown responses, there may be insufficient data to fully describe participant comorbidities that may confound the 'true' causal reason for an event.

Safety events outlined in Table 5 will be reported for both the Roctavian and SoC Cohorts.

Regarding the treatment policy estimand data analysis, the proportion of participants with each event will be calculated from index through the full follow-up period, without considering any intercurrent events. Given safety outcomes are event-based, for safety outcomes occur multiple times over the follow-up period (e.g., thromboembolic events), IPTW-weighted negative binomial regression models will be fit to compare safety outcomes between Roctavian and SoC Cohorts. For safety outcomes expected to occur once (e.g., death), IPTW-weighted log binomial regression models will be fit to compare safety outcomes between Roctavian and SoC Cohorts.

IPTW will be applied to create more similar Roctavian and SoC Cohorts. Other clinically significant prognostic factors or covariates that remain imbalanced after propensity score adjustment will be included in the model as well. Regression coefficients, corresponding 95% CIs and p-values will be reported for all explanatory variables included in the model. In the case that there are little to no events $n < 10$, that the relative risk log-binomial regression or negative binomial regression estimates are not stable, a logistic regression (which can approximate relative risk in a rare outcome⁵⁹) with firch correction will be conducted.

Under the hypothetical estimand data analysis, the event rate and incidence rate of each event will be calculated from index through the full follow-up period, where all participants will be included in analyses of event or incidence rates. Further, to compare Roctavian and SoC Cohorts safety outcomes under the hypothetical estimand, IPTW-weighted incident rate ratios (IRRs) will be estimated at the incident/event rate among the Roctavian Cohort divided by the incident/event rate among the SoC Cohort. See below for the event and incidence rate calculations:

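### For life-threatening bleeds the SAP has no rule for a cohort with zero events, and its fixed models then give no finite or valid Wald estimate

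*Protocol*

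**What the plan says.** SAP 7.9.4.1 compares the major, life-threatening and joint annualized bleeding rates with "an IPTW weighted negative binomial model or a IPTW weighted zero-inflated negative binomial model, whichever appropriate", chosen by the rules of SAP 7.9.3. Under those rules the zero-inflated model takes over "If the negative binomial model does not converge", or if it has the lower AIC. It is described as two parts: a binary model for any bleed, and a count model fitted only to participants who bled. For the primary rate ratio, the same section prescribes a Wald confidence interval.

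For the proportion of participants with zero bleeds, SAP 7.9.4.2 states: "The binary outcomes will be analyzed using propensity score IPTW weighted log binomial regression models". It names no fallback.

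The SAP does foresee sparse data, but only for safety outcomes. SAP 7.9.4.5 begins its rule with "In the case that there are little to no events", sets the threshold at n < 10, names unstable log-binomial or negative binomial estimates as the problem, and turns to logistic regression with a Firth correction. Neither bleeding section refers to that rule.

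**The concern.** Life-threatening bleeds are a subset of major bleeds, which are a subset of treated bleeds. With about 67 to 70 Roctavian participants, a cohort with no life-threatening bleed is a realistic outcome, more so in the 1-year analyses and in the subgroups to which SAP 7.9.5 applies the same methods. When one cohort has no events, the maximum likelihood rate ratio is zero, so its logarithm has no finite value. The log-binomial model for zero bleeds sits on the boundary, with a fitted proportion of 100% in that cohort. Inverse probability weights are positive multipliers, so a cohort total of zero stays zero after weighting.

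Two declared secondary endpoints built from the same bleeds could then carry estimates that mean nothing: one table suggesting no information at all, the other suggesting a precise difference. Both go into a benefit assessment.

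**Working it through.** **1. The plan's own figure.** Inputs from SAP 7.6: the rate ratio is "tested against the shifted null hypothesis of 0.5, assuming a significance level" of 2.5% one-sided, with 80% power, θ = 0.2, rates 3 and 0.85 per year, dispersion 1.5 and 1 year of exposure.
- V1 = 1/3 + 1/(0.2 × 0.85) + 1.2 × 1.5/0.2 = 15.216
- V0 = 1.1²/(0.5 × 0.2 × 3.17) + 9 = 12.817
- N1 = (1.960 × √12.817 + 0.842 × √15.216)² / (log 0.5 − log(0.85/3))² = 328.8

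This rounds to 329 + 66 = 395, against the stated 330 + 67 = 397. The cohort sizes are confirmed within rounding. They concern treated bleeds only; no document gives a rate for major or life-threatening bleeds.

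**2. How often the Roctavian cohort has zero events.** Assumption: SoC life-threatening rate of 0.005 to 0.01 per person-year. P(0) = exp(−67 × years × rate × ratio). The ratio 0.85/3 = 0.283 is the design value for treated bleeds, borrowed here.

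| Follow-up | No effect | Ratio 0.283 |
|---|---|---|
| 3 years | 13-37% | 57-75% |
| 1 year | 51-72% | 83-91% |

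**3. What the fixed models return.** Assumed illustration: 0/67 Roctavian and 10/330 SoC participants, one event each, 3 years, unweighted.
- Negative binomial, dispersion 1.5: log rate ratio −20.9, SE 14,544, Wald p = 0.999, with convergence reported. A second implementation, which estimates the dispersion, gives −17.8, SE 3,130, p = 0.995. A finite estimate is printed each time, so a trigger based on non-convergence may not fire.
- Two-part fallback: no Roctavian participant enters the count part. Its design has rank 1 of 2, so the treatment effect is not estimable. The binary part is separated.
- Log-binomial for zero bleeds: RR = 1/(320/330) = 1.031, log RR = 0.0308, SE = √(10/(330 × 320)) = 0.0097, z = 3.16, p = 0.0016. The Roctavian proportion, 67/67, contributes no variance at all.
- Fisher's exact test, two-sided: p = 0.224.
- Exact conditional upper 95% limit for the rate ratio: with q = 1 − 0.025^(1/10) = 0.308, q/(1 − q) × 990/201 = 2.2.
- Likelihood-ratio tests: p = 0.057 (negative binomial) and 0.053 (binomial).

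**4. Dependence on the assumed SoC count,** with zero Roctavian events throughout:

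| SoC participants with an event | Log-binomial Wald p | Fisher p |
|---|---|---|
| 3 | 0.083 | 1.00 |
| 5 | 0.025 | 0.59 |
| 8 | 0.0047 | 0.36 |
| 10 | 0.0016 | 0.22 |
| 15 | 0.0001 | 0.086 |

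The negative binomial Wald p stays near 0.999 over the 3 to 12 events fitted.

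**5. The SAP's own safety remedy on the same data.** Firth logistic regression gives an odds ratio of 0.23 with penalised likelihood-ratio p = 0.198, in line with Fisher. Its Wald p is 0.310.

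**The case against.** A reader might infer that the plan must yield p = 0.999 and p = 0.002 from the same data. The documents do not support that. The clash comes from Wald statistics; by likelihood ratio the two models agree at about 0.05. Wald is named only for the primary rate ratio's interval. Reading it into 7.9.4.1 through the inherited rules is fair, but 7.9.4.2 names no test. Robust standard errors, which 7.9.4.1 does not mention, would drive the negative binomial p to essentially zero. That shows how arbitrary the Wald result is here, and that 0.999 is not fixed by the SAP.

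A reader might also call the illustrated pattern likely. It rests on assumed rates. Zero Roctavian events together with at least 10 SoC events has a joint probability of 1-30% across the assumptions of step 2. With at least 5 SoC events it is 13-55%.

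The scope is limited too. Severe bleeds are defined by symptoms not ending within 24 hours, so major bleeds need not be rare. Zero events is unlikely for joint bleeds and implausible for treated bleeds.

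Some planned comparisons do not break. The table shells show counts and simple tests; on the illustration the chi-square p is 0.149. Protocol 10.3.7.1 follows the primary t-test approach (pooled p = 0.150, Welch p = 0.0015), a separate conflict with the SAP. SAP 7.9 also declares all secondary p-values nominal.

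These points narrow the finding. They do not supply a rule for a zero cell in 7.9.4.1 or 7.9.4.2, and they leave the specified adjusted models unusable when it occurs.

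**Conclusion.** The point holds for life-threatening bleeds and possibly for major bleeds, small subgroups and 1-year analyses. With zero events in one cohort, the specified models give no finite or valid Wald estimate. The fallback does not help: its trigger may not fire, and its count part cannot estimate the treatment effect. Zero events under Roctavian has a chance of 13-37% with no effect and 57-75% at a ratio of 0.283. Both ranges depend on the assumed rate of 0.5 to 1 per 100 person-years, and the second also on the borrowed ratio. The p-values are from unweighted fits; weighting would change them but not the separation. The harm is misleading secondary estimates. Error control on the primary endpoint is untouched. The change is worth making because the SAP already recognises the problem for safety outcomes.

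**What to change.** Extend the sparse-event rule of SAP 7.9.4.5 to 7.9.4.1 and 7.9.4.2. Trigger it by fewer than 10 events in total **or** zero events in either cohort, not by non-convergence. The zero-cell condition is needed because the illustration has exactly 10 events and would miss a threshold of fewer than 10. When triggered:

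- report event counts and rates by cohort;
- let an IPTW-weighted, Firth-penalised model for having one or more bleeds govern the comparison, with a penalised-likelihood (not Wald) interval and p-value;
- add an exact conditional rate ratio with its interval, labelled as unweighted and supportive;
- do not use the zero-inflated fallback.

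Modelling the event instead of its absence is not enough by itself: an unpenalised log-binomial model for one or more bleeds gives log RR −20.9 and p = 0.999 on the same data.

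The cost is a few sentences in the SAP, with no new data and no change to the primary analysis. There are two downsides. The penalised model gives an odds ratio, close to a risk ratio only while events are rare. The exact interval is not adjusted for confounding.
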